3.2 Secondary Objective(s)

The specific secondary objectives are:

(3) Neurobiological Mechanisms: Test the hypothesis that 4 months of web-based sleep education and CPAP will reduce a) astrocyte activation (plasma GFAP) b) neurofibrillary tangle burden (plasma pTau181) and c) MRI-visible perivascular space burden more than web-based sleep education alone.

(4) Sleep Physiology: Identify features of sleep physiology (i.e. decreased hypoxic burden and fragmentation, increased slow-wave power and REM sleep) that mediate the impact of CPAP on cognitive function.

4 STUDY DESIGN

4.1 General Design

The general design of this study is a single-blinded randomized controlled trial of 206 adults randomized into two groups:

Early CPAP group: Participants randomized to this group will start BHP-sleep and CPAP simultaneously and continue both for 8 months. BHP-sleep consists of the sleep modules of the Canadian Consortium on Neurodegeneration in Aging's (CCNA) online Brain Health PRO platform covering sleep physiology, healthy sleep habits, and information about sleep disorders like sleep apnea. Participants will receive a study-provided auto-titrating CPAP device, with settings set by one of the study sleep medicine physicians according to current clinical practice parameters. Participants will undergo an in-person mask fitting, and then will be supported by a sleep technologist with extensive clinical experience with CPAP.

Later CPAP group: Participants randomized to this group will start BHP-sleep without CPAP for first 4 months, followed by BHP-sleep and CPAP simultaneously for remaining 4 months of participation.

4.2 Primary Outcomes

The primary outcome of this study will be change in the Symbol Digit Modalities Test (SDMT). The SDMT is a test of speeded executive function that is predictive of clinically significant improvement in patients with MCI with a well-defined minimal clinically significant change (2) and that is responsive to CPAP in observational studies (3).

Additional cognitive measures that supplement the primary outcome of this study will be: attention and executive function (Trail Making Test A & B), working memory (Digit Span and Letter-Number Sequencing), verbal learning and memory (Hopkins Verbal Learning Test), and severity of cognitive impairment (Alzheimer's Disease Assessment Scale – Cognitive Subscale; ADAS-Cog-13).

4.3 Secondary Outcomes

Vascular risk factors and AD-biomarkers: Plasma pTau181 (for AD pathology) and GFAP (for astrocyte activation) will be assessed. pTau181 has been shown to be strongly predictive of both amyloid and tau pathology as measured by PET (4,5) while plasma GFAP correlates strongly with ¹⁸F-SMBT-1 PET, a marker of brain reactive astrocytes (6). This protocol does not include plasma amyloid beta 42 as recent studies suggest that pTau181 alone has similar performance to a larger panel of biomarkers in discriminating between levels of a PET proxy of AD pathology (4) and our previous work showed a stronger association between sleep fragmentation and burden of tau pathology than burden of amyloid pathology (7).

Aliquots will be sent to and analysed in the Toronto laboratory of Co-I [name] on the Quanterix SIMOA platform, a semi-automated digital ELISA platform. Analysis will include quantification of plasma p-tau-181 using the ptau-181 V2.1 Advantage assay, and GFAP using the GFAP discovery assay.

Remaining aliquots will be retained for future studies.

Blood levels of various fats, sugars, and proteins (like cholesterol or glucose) will be assessed.

Participants will undergo MRI using the Canadian Dementia Imaging protocol consisting of a 3D T1, interleaved 3mm PD/T2, 3D FLAIR, T2*, DTI, and resting state BOLD. Perivascular spaces and white matter hyperintensities will be quantified with the SynthSegCSVD algorithm developed and validated in our laboratory, a robust neural network based tool (Figure 4).

Sleep physiology will be assessed using wearable sensors: at-home sleep apnea testing apparatus (for oximetry metrics including AHI, ODI, mean SpO₂, hypoxia burden, and time with O₂<92%), EEG headband (sleep staging, including % slow wave sleep, % REM sleep, total EEG sleep time, and NREM slow wave power), and wrist-worn accelerometry (for total sleep time and sleep fragmentation).

5 PARTICIPANT SELECTION AND WITHDRAWAL

Community-dwelling older adults who respond to recruitment initiatives and advertisements, or patients attending dementia prevention clinics, memory clinics, or sleep clinics throughout the Greater Toronto Area. Target sample size is 206 adults over the age of 55 with MCI and previously untreated OSA.

5.1 Inclusion Criteria

Each participant must meet all of the following inclusion criteria to participate in this study:

- 1) Informed consent obtained and signed.
- 2) Age >55
- 3) MCI: Participants will undergo a video-based screening, including a clinical interview, Logical Memory II, MoCA, and Lawton-Brody Instrumental Activities of Daily Living Scale Score. A participant will be considered to have MCI if they have:
 - a. MoCA score of 13-24, and
 - b. Logical Memory II Score ≤ 8 (≥ 16 years of education), ≤ 4 (8-15 years of education) or ≤ 2 (0-7 years of education), and
 - c. Lawton-Brody IADL Score $>14/23$, and
 - d. do not meet DSM IV criteria for dementia, and
 - e. have a change in self-perceived cognition from previous
- 4) Moderate-severe OSA: Participants who screen positive for MCI will be mailed an at-home sleep apnea testing device (Apnealink, ResMed, San Diego, California, USA), an FDA-approved self-administered 3-channel portable device that assesses for sleep apnea based on airflow as assessed using an intra-nasal pressure transducer, pulse oximetry assessed using a finger probe, and respiratory effort using a band around the chest.. Participants with $ODI \geq 5$ will undergo in-lab polysomnography (PSG) for confirmation and characterization of sleep apnea. A participant will be considered to have moderate-severe OSA if they have on PSG:
 - a. $AHI \geq 15$, and
 - b. $ODI \geq 10$, and
 - c. central apneas $< 10\%$ of all apneas, and
 - d. periodic limb movement index < 15 .

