5.4 Participant Screening

Potential participants, irrespective of the recruitment source, will be required to proceed to the study website where they will fill out a short REDCap-hosted online questionnaire. The questionnaire will include collection of basic demographics and subjective sleep and cognitive information, limited to information necessary for determining eligibility. This includes email address, phone number, and implied consent to be contacted by study staff for additional screening.

Potential participants who fill out the REDCap-hosted online questionnaire will be contacted by study staff to assess eligibility. This includes:

- 1) An in-depth video-conference to establish a diagnosis of MCI and to confirm all inclusion/exclusion criteria. This will consist of a clinical interview, Logical Memory II, MoCA, and Lawton-Brody Instrumental Activities of Daily Living Scale Score, as well as screening for clinically significant insomnia (Insomnia severity index>15) or restless legs syndrome (Cambridge Hopkins questionnaire). 2) If MCI confirmed, participants will be mailed a home-based sleep apnea test (HSAT), namely the Apnealink which will be self-administered. With our community-based recruitment model, using a HSAT is necessary to minimize the number of participants without sleep apnea who need to undergo polysomnography. The Apnealink is considered a Type 4 sleep monitor by the American Academy of Sleep Medicine and has been validated against polysomnography. 3) Individuals who screen positive for OSA on the HSAT will meet with a study physician by video call or in person prior to in-lab PSG. The study physician will confirm inclusion and exclusion criteria, including positive results for both MCI and OSA, and will perform a standard clinical assessment to ensure clinical appropriateness of and eligibility for CPAP. The participant will then be scheduled for an in-lab PSG. 4) Participants that meet the criteria for MCI and OSA, and satisfy all other inclusion/exclusion criteria, will have a video-conference with study staff to discuss the final determination of eligibility, obtain informed consent, and to unlock their randomization assignment.

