5.5 Screen Failures

Participants that do not meet the criteria for MCI or OSA, or do not meet all of the inclusion criteria or have at least one of the exclusion criteria at any stage of the screening process are deemed as screen failures and will have a video-conference with study staff to discuss their

reason for not being eligible. These participants who have failed the screening criteria are ineligible for participation and will be informed that they do not meet the study's inclusion criteria and they will be thanked for their time. They will be encouraged to try to participate in future studies for which they may be eligible, and they will have an opportunity to ask questions pertaining to their screening for this study. Screen information will be retained as part of the trial for further analyses.

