7.2 Study Instruments

Copies of each study instrument can found in Appendix D.

7.2.1 *Eligibility Screening and Basic Information*

Screening Checklist for Eligibility: The screening checklist for eligibility is a simple document with inclusion and exclusion criteria. All inclusion criteria and no exclusion criteria must be met to be eligible (video conference). See Appendix C-1.

Demographic and Medical Information: Basic demographic and medical information include age, sex, education, and past/present medications and medical comorbidities. (video conference). See Appendix C-2.

7.2.2 *Sleep Disorders and Patient Reported Sleep Outcomes*

Sleep Apnea: As an initial screen for sleep apnea, we will use the STOP-Bang questionnaire completed on an online form (12). See Appendix C-3.

Insomnia Severity Index (ISI): A 7-item questionnaire assessing sleep onset, sleep maintenance, sleep satisfaction, and sleep problems. Each item is rated on a scale ranging from 0-4 with total scores ranging from 0 to 28 and higher scores suggesting more severe insomnia (13). The ISI is administered as a questionnaire which can be administered via any interphase (face-to-face or video conferencing). We will administer it via video conferencing. See Appendix C-4.

Restless Legs. RLS will be assessed using the 8-item Cambridge Hopkins Questionnaire (14) administered by video conference. See Appendix C-5.

REM Sleep Behaviour Disorder RBD will be assessed using a single question from the Mayo sleep questionnaire: “Have you ever been told, or suspected yourself, that you seem to ‘act out your dreams’ while asleep (for example, punching, flailing your arms in the air, making running movements, etc.)?” (15). See Appendix C-6.

Self-Report Sleep Quality: We will use the PROMIS Sleep Disturbance and PROMIS Sleep Related Impairment short form questionnaires to assess subjective sleep quality (16). See Appendix C-7.

Sleep Diary: We will use a 10-day sleep diary to complement the accelerometry data. See Appendix C-8.

7.2.3 *Cognitive Evaluation*

Montreal Cognitive Assessment: The Full MoCA via Audio-Visual Conference consists of a 30-point test assessing the following items: short term memory recall, visuospatial abilities,

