7.2.4 Functional Status

IADL: The Lawton-Brody Instrumental Activities of Daily Living (IADL) scale measures participant's ability to engage in instrumental activities of daily living via questionnaire assessing activities such as preparing meals and managing personal finances (25). Responses range from

0 (normal ability) to 3 (dependent for functioning) with total scores ranging from 0 to 23. This assessment of functional independence is collected via questionnaire, which can be administered via any interface (face-to-face or video conferencing). We will administer it via video conferencing. See Appendix C-17.

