APPENDIX C-1: INCLUSION/EXCLUSION LIST

INCLUSION CRITERIA	CRITERIA MET? (Should be Yes)		SUPPORTING SOURCE DOCUMENT	
			NAME OR LOCATION	DATE (mm-dd-yy)
Informed consent obtained and signed	 Yes	 No		
Age > 55	 Yes	 No		
MoCA score 13-24	 Yes	 No		
Logical Memory II score: ≤ 8 (if ≥ 16 years of education) ≤ 4 (if 8-15 years of education) ≤ 2 (if ≥ 0-7 years of education)	 Yes	 No		
Lawton-Brody IADL score >14	 Yes	 No		
DSM IV criteria for dementia not met	 Yes	 No		
Change in self-perceived cognition from previous	 Yes	 No		
Apnealink ODI ≥ 5	 Yes	 No		
PSG AHI ≥ 15	 Yes	 No		
PSG ODI ≥ 10	 Yes	 No		
PSG central apneas <10% of all apneas	 Yes	 No		
PSG periodic limb movement index <15	 Yes	 No		

EXCLUSION CRITERIA	CRITERIA MET?	SUPPORTING SOURCE DOCUMENT

	(Should be No)		NAME OR LOCATION	DATE (mm-dd-yy)
Drowsiness-related driving accidents or near misses in the past 12 months	 Yes	 No		
Drives as their primary occupation	 Yes	 No		
Unable to complete cognitive evaluation in English	 Yes	 No		
Unable to participate in video-based cognitive assessment	 Yes	 No		
Not a resident of Ontario	 Yes	 No		
Contraindications to MRI	 Yes	 No		
Contraindications to CPAP or unwilling to start CPAP	 Yes	 No		
No available study partner to support CPAP	 Yes	 No		
Previously treated for sleep apnea	 Yes	 No		
Clinically significant insomnia (ISI > 15)	 Yes	 No		

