APPENDIX C-17: LAWTON BRODY IADL

LAWTON - BRODY INSTRUMENTAL ACTIVITIES OF DAILY LIVING SCALE (I.A.D.L.)			
Scoring: For each category, circle the item description that most closely resembles the client's highest functional level (either 0 or 1).			
A. Ability to Use [contact]	E. Laundry	1 1 0
1. Operates telephone on own initiative-looks up and dials numbers, etc.	1	1. Does personal laundry completely	1
2. Dials a few well-known numbers	1	2. Launder small items-rinses stockings, etc.	1
3. Answers telephone but does not dial	1	3. All laundry must be done by others	0
4. Does not use telephone at all	0		
B. Shopping	1 0 0 0	F. Mode of Transportation	1 1 1 0 0
1. Takes care of all shopping needs independently	1	1. Travels independently on public transportation or drives own car	1
2. Shops independently for small purchases	0	2. Arranges own travel via taxi, but does not otherwise use public transportation	1
3. Needs to be accompanied on any shopping trip	0	3. Travels on public transportation when accompanied by another	1
4. Completely unable to shop	0	4. Travel limited to taxi or automobile with assistance of another	0
		5. Does not travel at all	0
C. Food Preparation	1 0 0 0	G. Responsibility for Own Medications	1 0 0
1. Plans, prepares and serves adequate meals independently	1	1. Is responsible for taking medication in correct dosages at correct time	1
2. Prepares adequate meals if supplied with ingredients	0	2. Takes responsibility if medication is prepared in advance in separate dosage	0
3. Heats, serves and prepares meals, or prepares meals, or prepares meals but does not maintain adequate diet	0	3. Is not capable of dispensing own medication	0
4. Needs to have meals prepared and served	0		
D. Housekeeping	1 1 1 1 0	H. Ability to Handle Finances	1 1 0
1. Maintains house alone or with occasional assistance (e.g. "heavy work domestic help")	1	1. Manages financial matters independently (budgets, writes checks, pays rent, bills, goes to bank), collects and keeps track of income	1
2. Performs light daily tasks such as dish washing, bed making	1	2. Manages day-to-day purchases, but needs help with banking, major purchases, etc.	1
3. Performs light daily tasks but cannot maintain acceptable level of cleanliness	1	3. Incapable of handling money	0
4. Needs help with all home maintenance tasks	1		
5. Does not participate in any housekeeping tasks	0		
Score		Score	
Total score _____			

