A summary score ranges from 0 (low function, dependent) to 8 (high function, independent) for women and 0 through 5 for men to avoid potential gender bias.

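### The mandatory IADL entry threshold (>14 of 23) cannot be applied under any scoring the protocol states: the appended form stops at 8, and the only 0-23 scale described runs towards dependence

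*Protocol*

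**What the plan says.** - **Section 5.1, criterion 3c** requires "Lawton-Brody IADL Score $>14/23". It is joined by 'and' to the other MCI sub-criteria, including 3d, that dementia criteria are not met.
- **Appendix C-1**, the eligibility checklist, has "Lawton-Brody IADL score >14", with no denominator and no direction.
- **Section 7.2.1** states that "All inclusion criteria and no exclusion criteria must be met to be eligible". Section 5.5 adds that people who miss a criterion "at any stage of the screening process are deemed as screen failures".
- **Section 7.2.4** describes responses running from "0 (normal ability) to 3 (dependent for functioning) with total scores ranging from 0 to 23". Higher therefore means more dependent. The section then refers to Appendix C-17 for the instrument.
- **Appendix C-17** tells the assessor to circle, for each of eight categories, the description nearest the person's "highest functional level (either 0 or 1"). Its footnote reads: "A summary score ranges from 0 (low function, dependent) to 8 (high function, independent) for women and 0 through 5 for men". Here higher means more independent.

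**The concern.** These places disagree on both the range and the direction of the same score, and a mandatory entry criterion depends on that score. Taken literally, the form makes the threshold unreachable. Section 7.2.4 makes it select for dependence, which pulls against the requirement that dementia be absent. The protocol gives no conversion between the two scales and no reversal of direction.

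At stake is a reproducible definition of the trial population. Screening staff could settle the conflict in different ways, eligibility could not be audited against the source form, and readers could not tell what level of function the results apply to.

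**Working it through.** **Inputs.** The threshold is >14 of 23 (Section 5.1). Section 7.2.4 gives a response range of 0-3 and a total of 0-23, with high meaning dependent. Appendix C-17 prints this many response options per item: A 4, B 4, C 4, D 5, E 3, F 5, G 3, H 3.

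**1. The form's own maximum.** Eight items with a highest printed score of 1 give 8 × 1 = 8, which reproduces the stated maximum for women. The maximum for men is stated as 5. Both are below 15, so 0% can pass on the form as printed.

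**2. Where 23 could come from.**
- Eight items each scored 0-3: 8 × 3 = 24, not 23. This assumes that every item reaches 3.
- C-17 options ranked from 0 but capped at 3: 3+3+3+3+2+3+2+2 = 21.
- C-17 options ranked in full, last option = 0: 3+3+3+4+2+4+2+2 = 23.

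Only full ranking gives 23. C-17 does not instruct it, and it takes items D and F to 4, outside the 0-3 range in Section 7.2.4.

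**3. What >14 admits in each direction of a 0-23 total, expressed as a dependence score.**
- High = dependent (Section 7.2.4): 15-23 passes. At the boundary that is 15/8 = 1.9 points per item, and a person with normal function (0) fails.
- High = independent: a score of 15-23 is a dependence score of 23 − 23 = 0 to 23 − 15 = 8.
- The two admitted groups do not overlap, and 9-14 fails in both directions.

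**4. Whether a printed C-17 total can be converted to the 0-23 scale.** All response patterns of the eight-item form were enumerated: 4·4·4·5·3·5·3·3 = 43,200. Each was scored both as printed (0/1) and by full ranking with high = independent.

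| Printed total | Ranked total, range | Patterns above 14 |
|---|---|---|
| 0 | 0-6 | 0 of 36 |
| 1 | 1-10 | 0 of 492 |
| 2 | 2-13 | 0 of 2,719 |
| 3 | 3-16 | 11 of 7,855 |
| 4 | 4-18 | 436 of 12,789 |
| 5 | 6-20 | 2,360 of 11,789 |
| 6 | 8-21 | 3,190 of 5,900 |
| 7 | 11-22 | 1,279 of 1,476 |
| 8 | 14-23 | 143 of 144 |

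The single failing pattern at 8 takes the lowest-ranked option that still scores 1 on every item: 1+3+3+1+1+2+2+1 = 14. Every printed total from 3 to 8 has patterns on both sides of 14, so no cut-off on the printed total reproduces the criterion. These are counts of possible patterns, not of people.

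**The case against.** Section 5.1 prints the denominator beside the threshold, so a careful screener would not compare an 8-point total with 14. C-17's options rank to exactly 23 and the form has the assessor circle a description for each item, so a total out of 23 can be derived from a completed form. The authors very probably meant that scoring, with high meaning independent. Conversion failures are also rare at the top of the printed scale: one pattern in 144 at 8/8. Criterion 3d limits enrolment of people with dementia, as does the physician review in Section 5.4 ("The study physician will confirm inclusion and exclusion criteria, including positive results for both MCI and OSA"). The mismatch would show at the first completed form.

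Much of this stands. The 0% figure applies to the form and checklist used as printed. The 24 rests on every item reaching 3, which Section 7.2.4 does not say. A scoring note on the existing form might serve as well as a new form. The safeguards against enrolling people with dementia are real.

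None of it makes the criterion usable as written. The scoring that would rescue it appears nowhere in the protocol, contradicts the direction and item range in Section 7.2.4, and contradicts the 0/1 instruction on the form. Noticing the mismatch does not supply a rule for resolving it, and the physician has to re-confirm the same undefined criterion.

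**Conclusion.** The concern holds. Each scoring that the protocol states either admits no one (C-17 as printed) or selects people with 15 or more of 23 dependence points (Section 7.2.4). The one reading that makes sense of the threshold has to be inferred.

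The consequence is confined to eligibility and to the description of the population. IADL is neither an outcome (Sections 4.2 and 4.3) nor a covariate in the primary model (Section 9.4), and eligibility is settled before the assignment is unlocked (Section 5.4), so the randomised SDMT comparison is not biased. The matter should be fixed, but it does not threaten the trial's primary inference.

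The conclusion rests on the printed text and on counting C-17's response options. The conversion check also assumes that all eight items are scored. The appendix does not say which items make up the total of 5 for men.

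**What to change.** Reconcile Sections 5.1 and 7.2.4 with Appendices C-1 and C-17. Name one scoring version, give its item scores, total range and direction, and attach a form or scoring instruction that produces that total. State the threshold with its denominator on that version, in the same words in Section 5.1 and Appendix C-1. If the chosen version scores men and women differently, say how the threshold applies to each. Which version and threshold apply is for the sponsor to decide.

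For anyone already screened, recompute the score from the option circled for each item, because the printed total alone is not enough.

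The cost is a wording amendment to Sections 5.1 and 7.2.4 and Appendix C-1, a replaced or annotated C-17, and an item-level re-check of existing screening forms. Design, sample size and analysis do not change.

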5.2 Exclusion Criteria

All potential participants meeting any of the following exclusion criteria will be excluded from participation in this study:

- 1) drowsiness-related driving accidents or near misses in the past 12 months
- 2) drives as their primary occupation
- 3) unable to complete cognitive evaluation in English
- 4) unable to participate in video-based cognitive assessment
- 5) not a resident of Ontario
- 6) contraindications to MRI

- 7) contraindications to CPAP or unwilling to start CPAP
- 8) no available study partner to support CPAP
- 9) previously treated for sleep apnea
- 10) clinically significant insomnia (ISI > 15), restless legs syndrome, or shift work
- 11) taking disease modifying agents for MCI

